Protocol specified 2 off-treatment chemistry values collected within the Week 52 (prior to protocol version 6), Week 104, Week 108 and Week 112 analysis window at A and B visits. At Week 52, Week 104, Week 108, and Week 112 visits, the 2 off-treatment measurements that are in the analysis window and closest to the target day specified in Table 4 are averaged for the purpose of data summary and analysis. All values included in the Week 103, 104, 108, and 112 analysis windows must also be assessed after last dose.

Records from visits not closest to the target study day, and therefore not used in analyses, are presented in by-patient data listings.

Table 4. ANALYSIS VISIT WINDOWS

Analysis Visit	Label	Target		Analysis Window
		Study Day ^a	Days After Last Dose	
1	Week 1	7	-	$2 \leq \text{study day} \leq 10$
2	Week 2	14	-	$11 \leq \text{study day} \leq 21$
4	Week 4	28	-	$22 \leq \text{study day} \leq 35$
6	Week 6	42	-	$36 \leq \text{study day} \leq 49$
8	Week 8	56	-	$50 \leq \text{study day} \leq 70$
12	Week 12	84	-	$71 \leq \text{study day} \leq 126$
24	Week 24	168	-	$127 \leq \text{study day} \leq 210$
36	Week 36	252	-	$211 \leq \text{study day} \leq 294$
48	Week 48	336	-	$295 \leq \text{study day} \leq 350$
52	Week 52	364	-	$351 \leq \text{study day} \leq 406$
64	Week 64	448	-	$407 \leq \text{study day} \leq 490$
76	Week 76	532	-	$491 \leq \text{study day} \leq 574$
88	Week 88	616	-	$575 \leq \text{study day} \leq 658$
100	Week 100 ^b	700	-	$659 \leq \text{study day} \leq 720$
103	Week 103 ^c	721	21	$721 \leq \text{study day} \leq 727^{\text{d}}$ or $21 \leq \text{after last dose} \leq 27^{\text{e}}$
104	Week 104 ^c	728	28	$728 \leq \text{study day} \leq 755^{\text{d}}$ or $28 \leq \text{after last dose} < 55^{\text{e}}$
108	Week 108 ^c	756	56	$756 \leq \text{study day} \leq 783^{\text{d}}$ or $56 \leq \text{after last dose} \leq 83^{\text{e}}$
112	Week 112 ^c	784	84	$784 \leq \text{study day} \leq 806^{\text{d}}$ or $84 \leq \text{after last dose} < 106^{\text{e}}$

^a Study Day is relative to the date of first dose (Section 6.5.1).

^b Week 100 is the end of the dosing interval and should coincide with the last dose.

^c Including off-treatment values only.

^d Analysis windows are based on study day for patients who discontinued treatment early. Analysis windows are based on days after last dose for patients who complete treatment. Last dose for analysis is the Week 100 dose.

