8.5.1. Secondary Efficacy Endpoint Analyses

The secondary efficacy endpoint of this study is the change from baseline in eGFR at Week 100 (i.e., the end of the first year of drug exposure). The change from baseline in eGFR for patients treated with bardoxolone methyl is compared with placebo at Week 100 using MMRM analysis, with BASE_eGFR as a covariate, and the following fixed factors: treatment group (TRT), time (i.e., VISIT; analysis visit number), and the interaction between treatment and time (TRT x VISIT).

The trial design separates discontinuation of study drug from discontinuation of study follow-up. Therefore, patients may discontinue early from study drug while continuing follow-up with study visits and assessments. The analysis of eGFR at Week 100 uses available eGFR values irrespective of whether or not a patient is receiving treatment. Analyses for Week 100 will not include the Week 52 data due to mix of on-treatment and off-treatment values. The MMRM analysis uses all eGFR values collected through Week 100 according to analysis visits 1, 2, 4, 6, 8, 12, 24, 36, 48, 64, 76, 88, and 100 (Section 6.5.2). An unstructured covariance matrix is used. In the event the MMRM model with an unstructured covariance structure does not converge, the following covariance structures are substituted, in the order listed. Each subsequent covariance structure is used only if each no previous model did not converge.

1. Heterogeneous Toeplitz covariance structure (assuming different variances at each time point and measurements taken closer together in time are more highly correlated than those taken farther apart).
2. Toeplitz covariance structure (assuming measurements taken closer together in time are more highly correlated than those taken farther apart).
3. First order auto-regressive [AR(1)] covariance structure (assuming measurements taken closer together in time are more highly correlated than those taken farther apart, but the correlation is more constrained than the Toeplitz structure).
4. Compound symmetry covariance structure (assuming equal correlation for measurements from a patient, regardless of how far apart in time they were taken).

If the MMRM model does not converge using any of the aforementioned covariance structures, variables from the model statement may be removed in the sequence of 1) Tolv_STRAT, 2) ACR_STRAT.

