The difference between bardoxolone methyl and placebo in change from baseline in eGFR is estimated along with the 95% confidence interval at Week 100 for the primary analysis of the secondary endpoint.

Missing eGFR data will not be imputed.

SAS example as follows:

```
proc mixed data=OUT2 method=reml alpha=0.05 covtest;  
  class VISITNUM(ref=LAST)  
        TRT(ref=FIRST) SUBJID ACR_STRAT;
```

```
model DELT_eGFR = BASE_eGFR ACR_STRAT TRT VISITNUM  
          TRT*VISITNUM BASE_eGFR*VISITNUM / solution ddfm=kr;  
repeated VISITNUM / subject=SUBJID type=un r;  
lsmeans TRT*VISITNUM / pdiff om cl e;  
estimate 'Estimate at Week 100' TRT 1 -1 TRT*VISITNUM 1 -1 / cl;  
ods output LSMeans=LSM diffs=Diff;
```

run;

[figure not shown]
A plot of least squared means from the MMRM model at each visit by treatment arm will be created.

[figure not shown]

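### The SAS line labelled as the Week 100 estimate is coded on the first visit and returns the Week 1 treatment difference

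*SAP*

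**What the plan says.** SAP 8.5.1 analyses change from baseline in eGFR with an MMRM and takes the treatment difference and its 95% confidence interval at Week 100 as the main analysis of the secondary endpoint. The data enter "according to analysis visits 1, 2, 4, 6, 8, 12, 24, 36, 48, 64, 76, 88, and 100", which is 13 visits.

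The parts of the SAS example that matter here are:

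- The CLASS statement opens with "class VISITNUM(ref=LAST" and continues with "TRT(ref=FIRST) SUBJID ACR_STRAT". VISITNUM therefore comes before TRT.
- The MODEL statement ends with "TRT*VISITNUM BASE_eGFR*VISITNUM / solution ddfm=kr".
- LSMEANS requests all pairwise differences among the treatment-by-visit cells.
- The contrast is "estimate 'Estimate at Week 100' TRT 1 -1 TRT*VISITNUM 1 -1 / cl".
- The stored output is "ods output LSMeans=LSM diffs=Diff". The table that ESTIMATE produces is not stored.

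Two other statements in the section do not fit the rest of the SAP. The text describes Week 100 as "i.e., the end of the first year of drug exposure", whereas a footnote to Table 4 in SAP 6.5.2 says "Week 100 is the end of the dosing interval and should coincide with the last dose", at target Day 700, and SAP 8 speaks of two years of treatment. The text model lists baseline eGFR, treatment, visit and treatment by visit only; the baseline-by-visit interaction appears in the code alone and is not in Table 9.

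**The concern.** In PROC MIXED, the coefficients given for an effect in an ESTIMATE statement fill that effect's columns from the left, and the remaining columns get zero. The pair after `TRT*VISITNUM` has no leading zeros, so it acts on whichever cells come first. If those are the Week 1 cells, the label is wrong.

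The failure would be silent, because the contrast is estimable and prints a plausible estimate and interval. Week 1 (window Days 2 to 10) is also a very different quantity from Week 100 (window Days 659 to 720): by the schedule, patients are still on the starting dose at Week 1. The code could spread too, since SAP 9 allows continuous safety parameters to be summarised with the 8.5.1 method.

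**Working it through.** **Inputs.** 13 visit levels and the CLASS, MODEL and ESTIMATE statements come from SAP 8.5.1. There are two arms. Windows and target days come from Table 4 in SAP 6.5.2. The column-order and `ref=` rules are standard PROC MIXED behaviour and are not stated in the SAP: the reference level goes last, crossed effects follow CLASS order, and the rightmost CLASS variable varies fastest.

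**Column positions.** The treatment-by-visit effect has 13 × 2 = 26 columns. With visit varying slowest, the cell for the v-th visit and a-th arm is in column 2(v − 1) + a.

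| Cell | v | Columns |
|---|---|---|
| Week 1, arms 1 and 2 | 1 | 1, 2 |
| Week 2, arms 1 and 2 | 2 | 3, 4 |
| Week 100, arms 1 and 2 | 13 | 25, 26 |

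`ref=LAST` leaves Week 100 in last place, so it does not move the Week 100 cells to the front.

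**What the line estimates.** Write τ for the treatment effects and γ for the interaction. The between-arm difference at visit v is D(v) = (τ₁ − τ₂) + (γᵥ₁ − γᵥ₂); the visit, ACR, baseline and baseline-by-visit terms cancel. The line as written gives (τ₁ − τ₂) + (γ₁₁ − γ₁₂), which is D at Week 1. The Week 100 contrast needs 2 × 12 = 24 zeros before the pair.

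**Check on the full design.** The over-parameterised design has 1 (intercept) + 1 (baseline) + 2 (ACR) + 2 (treatment) + 13 (visit) + 26 (treatment by visit) + 13 (baseline by visit) = 58 columns. Its rank is 26 + 1 + 13 = 40. The vector in the SAP is identical to the Week 1 between-arm contrast; with 24 leading zeros it is identical to the Week 100 contrast. Both are estimable, and no effect size is assumed.

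**Illustration.** In simulated data with an assumed treatment difference of 10 − 0.07 × week, fitted by least squares (the covariance structure does not change which contrast the vector defines):

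| Coding | Result | Fitted Week 1 | Fitted Week 100 |
|---|---|---|---|
| As in the SAP | 8.903 | 8.903 | 2.219 |
| 24 leading zeros | 2.219 | 8.903 | 2.219 |

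These values only show which contrast is returned; they predict nothing about this trial.

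**Other orderings.** If VISITNUM sorted as text, the order would be 1, 100, 12, 2, … 8, 88, and the line would still return Week 1. If TRT came first in CLASS, the pair would fall on one arm at Weeks 1 and 2 and would not be estimable. None of the orderings tried gives Week 100.

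**Sign.** `ref=FIRST` moves the first-sorted arm to last place. If placebo sorts first (for example 0/1 coding), the line is bardoxolone minus placebo; if bardoxolone sorts first, the sign reverses. The SAP does not give the coding, although the hypotheses in SAP 8.2 are written as bardoxolone minus placebo.

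**Size of the error.** It is D(Week 1) − D(Week 100). Neither is given for this trial. The target days are 700 − 7 = 693 days apart.

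**Saved output.** The table of differences has 26 × 25 / 2 = 325 rows. Of these, 13 compare the arms at the same visit and 1 is the Week 100 comparison.

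**Text against code.** Without the baseline-by-visit interaction the rank is 26 + 1 + 1 = 28, so the code fits 40 − 28 = 12 more parameters than the text describes.

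**The case against.** The block is introduced as an example, and the sentence before it correctly asks for the difference at Week 100. The program stores the LSMEANS and their differences, and the Week 100 comparison there is right and shows which arm is subtracted from which. The faulty row appears only in printed output, and nothing in the SAP names it as the reported result. SAP 8.3 makes every significance level nominal and descriptive, and SAP 2 records that clinical development had already been stopped.

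All of that is true, and it limits the consequence. It does not make the line correct. One run would produce two different numbers that both claim to be the Week 100 difference, and the one carrying the explicit label would be wrong.

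A second objection concerns the repair. Adding 24 zeros is right only if VISITNUM is numeric and all 13 visits are present; under text sorting the last level is Week 88, so the repaired line would return Week 88. SAP 8.5.1 describes the variable as a visit number and Table 4 lists numeric values, so numeric coding is likely, but the condition should be stated. Naming the row of the saved differences works under any coding.

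The wording about the first year is clerical. The interaction mismatch is a separate point, though it does touch the saved result; its effect on the estimate is not known.

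**Conclusion.** The point holds. As coded, the line labelled Week 100 returns the Week 1 between-arm difference, given standard PROC MIXED ordering and the CLASS order shown. If that row were reported, the secondary endpoint would be misstated by the Week 1 difference minus the Week 100 difference, which could overstate or understate the Week 100 result; the documents do not allow it to be sized. No confirmatory conclusion is at stake, the estimand is correctly defined in the prose, and the correct contrast is in the saved output. It should still be corrected, because the error is silent and the SAP is the governing analysis document.

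**What to change.** 1. Delete the ESTIMATE line and state that the reported result is the Week 100 bardoxolone-minus-placebo row of the saved differences. Alternatively, put 24 zeros before the pair in `TRT*VISITNUM`, and state that VISITNUM is numeric with all 13 visits present.
2. State the TRT coding, so that the sign is bardoxolone minus placebo, in line with SAP 8.2.
3. Change the description of Week 100 to the end of the planned two-year treatment period.
4. Either add the baseline-by-visit interaction to the text model and Table 9, or remove it from the code.

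The cost is one line of code, a statement of the coding and two short text edits. No new data are needed.

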8.6.1.2. Off Treatment eGFR ANCOVA Analyses – No Imputation for Missing Data

The ANCOVA analysis (defined in Section 8.4.1) will be performed by using eGFR values collected at [redacted] Week 112 off-treatment analysis visits (Table 4). Missing eGFR data per visit are not imputed.

The difference between bardoxolone methyl and placebo in change from baseline of eGFR is estimated along with the 95% confidence interval at each off-treatment visits.

[figure not shown]

[REDACTED]

[REDACTED]

[REDACTED]

9. SAFETY AND TOLERABILITY

Safety and tolerability are evaluated by AEs, SAEs, clinical laboratory test results, body weight, vital signs, 12-lead ECG findings. All analyses of the safety data are performed using the safety analysis set. Descriptive statistics are presented by treatment group assignment in the safety analysis set. Statistical testing is not performed for safety analyses unless otherwise specified. On-treatment values are summarized according to the analysis study windows in Section 6.5.2; Off-treatment values are summarized according to the analysis study windows in Section 6.5.2.1. Safety data summaries are grouped by treatment.

Continuous safety parameters (including selected clinical chemistries and vital signs) may be summarized using the methodology described in Section 8.4.1, and Section 8.5.1. Only the visit windows outlined in Table 4 and Table 5 are included in these analyses.

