### 7.3. Treatment Assignment and Dosing Rationale

Patients will be randomized 1:1 to either bardoxolone methyl or placebo. Randomization will be performed using an interactive web response system (IWRS). Patients randomized to placebo will remain on placebo throughout the study but will follow sham titration to maintain the blind.

The use of a placebo comparator is justified because the known safety profile of tolvaptan (approved for the treatment of ADPKD in adults with evidence of rapidly progressing disease) pertaining liver toxicity would interfere with known pharmacologic effects of bardoxolone methyl on aminotransferases increase without liver toxicity, and complicate safety monitoring and medical management of patients in a double-blind trial. A placebo-controlled trial with bardoxolone methyl provides the best opportunity to determine the benefit-risk profile for bardoxolone methyl in ADPKD patients. A dose-titration regimen is being utilized to allow for individual dose optimization based on tolerability and based on the anticipated maximally efficacious dose of bardoxolone methyl, which may vary based on a patient's proteinuria status at baseline. Based on results from prior trials in patients with type 2 diabetes and CKD, Reata has concluded that higher bardoxolone methyl doses may be required to have an optimal effect on eGFR following drug withdrawal in patients with macroalbuminuria. Specifically, eGFR improvements in patients with normo- or micro-albuminuria were observed with a 20 mg bardoxolone methyl dose and the effects were retained following a 1-month withdrawal. In patients with macroalbuminuria, a 30-mg dose was required to produce a response that was similar to the patients with microalbuminuria treated at 20 mg. Consequently, the study includes dose titration up to a maximum dose of 20 mg for patients with  $ACR \leq 300$  mg/g and a maximum dose of 30 mg for patients with  $ACR > 300$  mg/g, as described below. The same dose titration regimen was used in a Phase 2 trial in adult ADPKD patients (study 402-C-1702). From a safety perspective, the 30 mg dose may be associated with an increased incidence of nausea; however, the nausea experienced in previous trials is generally mild, transient, and clinically manageable.

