4. STUDY DESIGN

4.1. Summary of Study Design

This international, multi-center, randomized, double-blind, placebo-controlled Phase 3 trial will study the safety, tolerability, and efficacy of bardoxolone methyl in qualified patients with ADPKD. Approximately 850 patients will be enrolled.

Patients will be randomized 1:1 to either bardoxolone methyl or placebo. Randomization will be stratified by eligibility eGFR category (30 to <60; ≥ 60 to 90), concomitant tolvaptan use (yes, no), and screening albumin to creatinine ratio (ACR; ≤ 300 mg/g, >300 mg/g). Patients randomized to placebo will remain on placebo throughout the study, undergoing sham titration. Patients with eGFR 60 to 90 mL/min/1.73 m² at screening should not comprise more than approximately 40% of enrolled patients.

The maximum bardoxolone methyl dose will be determined by baseline proteinuria status. Patients with baseline ACR ≤ 300 mg/g will be titrated to a maximum dose of 20 mg, and patients with baseline ACR >300 mg/g will be titrated to a maximum dose of 30 mg. Patients receiving bardoxolone methyl will start with once-daily dosing at 5 mg and will dose-escalate to 10 mg at Week 2, to 20 mg at Week 4, and then to 30 mg at Week 6 (only if baseline ACR >300 mg/g) unless contraindicated clinically and approved by the medical monitor. Dose de-escalation is permitted during the study if indicated clinically, and subsequent dose re-escalation is also permitted to meet the dosing objective of the highest tolerated dose.

[figure not shown]
All patients in the study will follow the same visit and assessment schedule. Following randomization on Day 1, patients will be scheduled to be assessed during treatment at Week 1, 2, 4, 6, 8, 12, 24, 36, 48, 52, 64, 76, 88, and 100 and by telephone contact on Day 3, 10, 21, 31, 38, and 45. Patients will continue study drug treatment through Week 100. Patients will also be scheduled to be assessed at an in-person follow-up visit at Weeks 103, 104, 108, and 112, after the end of treatment, respectively. The Data Monitoring Committee performs quarterly reviews of unblinded data for safety throughout the study.

Efficacy endpoints will be analyzed after all enrolled patients have completed the study and the final database lock.

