4.4. Randomization

Patients will be randomized 1:1 to either bardoxolone methyl or placebo. Randomization will be performed using an interactive web response system (IWRS) and will be stratified by eligibility eGFR category (30 to <60; ≥60 to 90 mL/min/1.73 m²), concomitant tolvaptan use (yes, no), and screening ACR (≤300 mg/g, >300 mg/g). Eligibility eGFR is the average of the screening eGFR visits. Patients randomized to placebo will remain on placebo throughout the study, undergoing sham titration.

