6.3. Analysis Populations

Table 3 lists the analysis populations in the study.

Table 3: ANALYSIS POPULATION DEFINITION

Analysis Population	Definition
ITT (Intent-to-Treat)	All enrolled patients categorized by their randomized treatment group (whether or not they received study drug).
Safety	All enrolled patients who received at least 1 dose of study drug. The safety population is used for evaluation of safety variables. Patients who received 1 dose of bardoxolone methyl will be classified in the bardoxolone methyl group. Patients who received at least 1 dose of placebo and no dose of bardoxolone methyl will be classified in the placebo group.

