8.1. General Considerations

Data collected from individual study centers will be pooled; results will not be presented by individual study center. Analyses are performed for all bardoxolone methyl patients in comparison with all placebo patients. Summary statistics for observed values, change from baseline, and percent change from baseline are presented by randomized treatment group. Missing values are handled as described in Section 6.6.

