9.1.2. Summaries of Adverse Events

Treatment-emergent adverse events and OTEAEs are summarized by treatment. For each treatment, SOC, and PT, the number and percentage of patients reporting an event is calculated. In summary tables, SOC is presented alphabetically and events within each SOC are presented by decreasing frequency count. Additionally, summary tables of events within PTs are presented by decreasing frequency count may be generated.

Summary tables (number and percentage of patients and events) of TEAEs (by SOC and PT) are provided by treatment as follows:

- All TEAEs
- All related TEAEs (definitely, probably, or possibly related)
- All TEAEs by severity
- All serious TEAEs (including deaths)
- All non-serious TEAEs
- All related serious TEAEs (including deaths)
- All TEAEs leading to permanent discontinuation of study drug
- All TEAEs leading to study drug interruption
- All TEAEs leading to dose de-escalation
- TEAEs by time to onset (≤ 12 weeks and > 12 weeks)
- TEAEs exhibited in $> 5\%$ of patients in either treatment group

Listings are provided showing:

- All AEs
- Deaths
- SAEs
- AEs leading to permanent discontinuation of study drug
- TEAEs leading to study drug interruption
- TEAEs leading to dose de-escalation

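### Most planned safety tables pool the 20 mg-target and 30 mg-target regimens, so a harm confined to the 30 mg regimen would appear only in proportion to the share of patients with ACR above 300 mg/g.

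*SAP*

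**What the plan says.** Safety and tolerability is a primary objective (Protocol 6.1.1, SAP 3.1.1). On dosing, SAP 4.1 states: "The maximum bardoxolone methyl dose will be determined by baseline proteinuria status". The cut is 300 mg/g, with a maximum of 20 mg at or below it and 30 mg above it. On allocation, SAP 4.4 states: "Patients will be randomized 1:1 to either bardoxolone methyl or placebo". The stratification factors there include "concomitant tolvaptan use (yes, no), and screening ACR", again cut at 300 mg/g. Protocol 7.3 notes that "the 30 mg dose may be associated with an increased incidence of nausea", and describes the nausea seen before as mostly mild and manageable.

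For analysis, SAP 9 says "Safety data summaries are grouped by treatment" and SAP 9.1.2 says "Treatment-emergent adverse events and OTEAEs are summarized by treatment". Treatment here means two groups. In SAP 6.3, "Patients who received 1 dose of bardoxolone methyl will be classified in the bardoxolone methyl group", and those who took only placebo form the other group. The laboratory (9.5.1), vital-sign (9.7) and ECG (9.9) summaries follow the same grouping.

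Dose appears in three places:
- SAP 9.5.2.1 splits the liver threshold table by maximum dosage received.
- SAP 9.2 tabulates exposure by dose and visit.
- SAP 7.3 allows, but does not require, baseline tables by randomised dose level.

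**The concern.** Two regimens are being tested in two groups of patients. Because randomisation is stratified on ACR, each regimen has concurrent, sham-titrated placebo patients from its own stratum. The protocol itself expects at least one tolerability problem to be commoner at the higher dose. Averaging both regimens into one active column means that an excess confined to the 30 mg regimen is spread over patients who were never eligible for that dose.

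The liver table does not close the gap, even for transaminases. Maximum dosage received is determined after randomisation, and Protocol 9.1.2 and 9.11 allow escalation to be slowed when ALT or AST rises early. A patient with a 30 mg target whose titration stops for that reason falls into a lower-dose row. The text also does not say how placebo patients are placed in that table. The exposure summary counts patients by dose but reports no harms.

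**Working it through.** **The plan's own figure.** The documents give no number for the safety tables or for the size of the ACR strata. The only sample-size figure is for efficacy (SAP 4.3.1): 850 patients, difference 2.3, SD 12, two-sided 0.05, about 80% power. With 425 per arm, 2.3 / (12 × √(2/425)) = 2.79, and 2.79 − 1.96 = 0.83, which gives 79.8%. It reproduces, but has no bearing on this point beyond fixing 425 per arm.

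**Dilution.** Let s be the share of patients with ACR above 300 mg/g. Stratified 1:1 allocation makes s about equal in both arms, so

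pooled excess = s × (excess with 30 mg target) + (1 − s) × (excess with 20 mg target).

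The values of s and the event rates are assumptions; none is in the documents. With a 10-point excess in the 30 mg regimen and none in the 20 mg regimen:

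| s | Pooled excess | Excess in the ACR >300 stratum |
|---|---|---|
| 15% | 0.15 × 10 = 1.5 points | 10 points |
| 20% | 0.20 × 10 = 2.0 points | 10 points |
| 30% | 0.30 × 10 = 3.0 points | 10 points |

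**Precision at s = 20%.** The stratum then has 0.20 × 425 = 85 patients per arm. Take a background rate of 10%.
- Stratum: 20% vs 10%, SE = √(0.20×0.80/85 + 0.10×0.90/85) = 5.4 points, ratio 10/5.4 = 1.8.
- Pooled: 12% vs 10%, SE = √(0.12×0.88/425 + 0.10×0.90/425) = 2.1 points, ratio 2/2.1 = 0.9.

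SAP 9 plans no safety tests unless otherwise specified, so these ratios show only how visible the excess would be.

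**If the 20 mg regimen also carries harm.** With excesses of 15 points (30 mg target) and 5 points (20 mg target) and s = 20%, the pooled figure is 0.20 × 15 + 0.80 × 5 = 7.0 points. It then describes neither regimen.

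**Small strata.** SAP 8 uses the ACR stratum as a covariate only if the smaller category exceeds 20% of patients, so a smaller share is contemplated. At 5% or 10% the stratum would have about 21 or 42 patients per arm, and its estimates would be very imprecise.

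**The case against.** The strongest reply is that nothing here is an error. Patients are randomised to drug or placebo, not to a dose. The intervention is one ACR-guided titration strategy, for which a table by treatment is the natural main display, and no section promises dose-specific safety tables. This stands, and it is why the pooled tables should stay.

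A reader might infer that pooling biases the safety comparison, that every safety table pools, or that the trial could not describe the 30 mg regimen at all. The documents support none of these. The overall contrast remains randomised and is simply an average over both regimens. The liver threshold table is split by dose received. Adverse events, including those leading to discontinuation, interruption or de-escalation, are listed by patient (SAP 9.1.2), and further analyses may be added as ad hoc (SAP 2). Section 9.6 is not in the available text and parts of Section 8.6 are redacted, so an existing split cannot be excluded.

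A reader might also take a difference between the strata as a dose effect. It is not: dose is fully confounded with albuminuria across strata. Nor do the strata map perfectly onto target dose. Stratification uses screening ACR, the maximum dose follows baseline ACR, and SAP 6.5.5.1 warns that the two may differ. The assessment schedule shows only one ACR collection before dosing, at Screen B, so they should usually agree.

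The sizes above are assumed, and zero excess at 20 mg is the case most favourable to the point. The fluid overload signal described in Protocol 5.1.2.1 came from a Phase 3 trial that used 20 mg (Protocol 5.1.1). Finally, sites were told on 10 May 2023 that development was ending, and SAP 8.3 now treats all objectives as descriptive, which lowers the urgency.

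**Conclusion.** The point holds as a gap in presentation, of minor severity. In the available text, the adverse event, general laboratory, vital-sign and ECG summaries do not show either regimen against its own stratum's placebo patients, although the stratified randomisation supports that comparison. The result is dilution, not bias. For a harm confined to the 30 mg regimen, the pooled excess is the stratum excess multiplied by the share with ACR above 300: an assumed 10 points becomes 1.5 to 3.0 points at an assumed 15-30% share. The multiplication is exact under those assumptions, but the true share and event rates are unknown. The dilution is relatively smaller where the 20 mg regimen also carries some of the harm. Drug against placebo within a stratum describes a regimen in the patients assigned to it; it does not isolate the effect of dose.

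**What to change.** Keep all pooled tables. In SAP 9 and 9.1.2, add descriptive versions of the key tables by randomised arm within ACR_STRAT, so that each regimen is set against placebo patients from its own stratum. The tables are: all TEAEs; serious TEAEs; TEAEs leading to interruption, de-escalation or discontinuation; transaminases; BNP; and weight.

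Report the number of patients whose ACR_STRAT differs from the baseline ACR category that set their target dose. State that differences between strata mix dose with albuminuria and are not a pure dose effect. If Section 9.6 already provides such tables, a cross-reference is enough.

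The cost is a few lines of SAP text and repeat runs of existing table programs by a variable already defined in SAP 6.5.5.3. No new data, tests or changes to dosing are needed. The downside is imprecision in the smaller stratum, more so if enrolment stopped short of 850.
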